Determine whether NutraStem® in combination with an exercise stimulus will cause increased human peripheral blood sample levels of CD34+ and CD133+ adult stem cells and whether these stem cells display more protection against oxidative stress.

B. Background and Significance

A stem cell is a specialized kind of cell that has a unique capacity to renew itself and to give rise to specialized cell types. These cells are found in many organs of the adult human including bone marrow, peripheral blood, umbilical cord blood, spleen, tooth pulp, adipose tissue, and brain. Stem cell research is currently a popular subject in the media and science (1). While stem cell therapies have been promised to offer important new treatments for a wide variety of illnesses, these therapies remain controversial and may take years to reach the medical market place due to the lengthy and costly regulatory requirements. Fortunately, a growing body of evidence suggests that there are numerous stem cells continually being produced within the human body throughout the lifespan. These stem cells are located in many different tissues and can become or "differentiate" into virtually any cell type within the body. Internal or endogenous stem cells are crucial to the body's ability to repair itself of degenerating tissues, or to replace cell populations, such as those destroyed by injuries, diseases, disorders, or treatments such as chemotherapy. Healthy stem cells are vital for the body's own natural regeneration and repair mechanisms to function. During natural aging, adult stem cells are known to have a reduced restorative capacity (2, 3) resulting in a reduced ability of the body to heal itself. However, a rapidly growing body of literature now indicates that certain nutrients, vitamins, and flavonoids could have important roles in the proliferation and replacement of stem cells required for healthy self-renewal of mature cells in the blood, brain, and other tissues (4-7). Thus, it appears possible to use certain natural products, either alone or synergistically, for the treatment of conditions where the stem cell replacement appears warranted.

C. Preliminary Studies

Preliminary studies establishing the effect of NutraStem® to increase proliferation of human adults stem cells and to demonstrate a homing effect in

[figure not shown]
[figure not shown]

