VISIT 1	informed consent, demographic information collected, BP screening, diabetes screening, resting blood draw, exercise intervention, post exercise intervention blood draw, receive NutraStem or placebo	40 to 80 minutes	\$40.00 * \$20.00 if unable to complete session for any reason
Visit 2	resting blood draw, exercise intervention, post intervention blood draw	45 minutes	\$60.00 * \$20.00 if unable to complete session for any reason
Visit 3	resting blood draw, exercise intervention, post intervention blood draw,	45 minutes	\$80.00 * \$20.00 if unable to complete session for any reason

Blood Analysis:

A 10ml Lavender top with EDTA tube of collected blood will be processed for MNC's and designated for flow cytometry to measure the stem cells including CD34+ and CD133+ cells at all blood draw time points. [name] will complete this portion of the analysis. A 5 ml SST tube will be collected for a lipid panel on the 1st blood draw of each session and delivered by the coordinator to Quest Lab for analysis. One additional tube of 5 cc's will be processed for serum measurements of biomarkers of inflammation and oxidative stress by the sponsor. These measures (IL1 β , IL4, IL6, hsCRP) will be completed by the sponsor. De-identified serum samples will be stored by [name] lab in a locked -80 freezer on the 5th floor of CBH until the sponsor specified time points of the study and then shipped to the sponsor following IATA Dangerous Goods Regulations by [name] lab personnel.

Blood sample collection tubes will be pre-labeled by the pharmacist doing the study drug/placebo randomization. The following randomization system will be used for the samples collected during this study:

Identifier (randomized to active ingredient or placebo)	Subject number	Study	Visit	Blood Draw	Description of Blood Draw
JKSB	01	01	01		Pre-exercise
JKSB	02	02	02		Post-exercise
JKSB	03	03	01		Pre-exercise
JKSB	03		02		Post-exercise
JKSB	04			01	Pre-exercise
				02	Post-exercise

Therefore, subject 17 on visit 3 for the post-exercise blood draw would be coded as:
JSKB170302

Subject 5 for visit 1 and pre-exercise blood draw would be coded as:
JSKB050101

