All quantifiable results will be expressed as mean \pm sem and will be analyzed using repeated measures Analysis of Variance (ANOVA). All post-hoc tests will be conducted using a Scheffè test. Only de-identified data will be sent to the sponsor for completion of data analysis. Subject data will be maintained by the study coordinator in a locked cabinet in CBH 508. Electronic databases will be maintained on a password protected computer. The study coordinator will create and maintain a password protected Excel master list that will contain study participants names, demographic information, study ID, and information recorded during the study sessions. Flow Cytometry results will be submitted to the research coordinator and forwarded from her to the sponsor. Data forwarded to the sponsor will be de-identified.

F. Human Subjects

Up to 60 men and women, generally healthy, age 50 to 70 with no debilitating (defined as having a chronic disease or condition that has severely limited activities of daily living, normal function, or ability to live an active life or injury). The study coordinator will explain the purpose of the study and describe all visit activities to potential participants. If they are still interested in the study they will be asked questions about their health to determine whether they are able to safely participate in the study. The “screening script” is a written tool based on the inclusion & exclusion criteria that will be used to screen all potential participants.

Inclusion Criteria

- Men or women who are 50 to 70 years of age, inclusive, at the baseline visit.
- Ability to do 15 minutes of treadmill walking exercise.
- Generally healthy

Exclusion Criteria

Subjects who meet any of the following exclusion criteria are not eligible for participation in this clinical research:

- Men and women less than age 50 or more than age 70
- Self reported history of difficult veins/difficulty obtaining blood samples
- Participated in more than 2 sessions per week of strenuous exercise in the last month
 - Are unwilling to follow the procedures of the trial, such as making visits or taking the supplements when asked to;
 - Are unable to tolerate the ingredients in NutraStem® or placebo, or who self report food allergies

- Have unintentionally lost or gained 10 or more pounds of body weight in the last 3 months;
- Have an acute illness (such as a severe cold or flu) or have been hospitalized within the past month.

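### The analysis plan ranks no outcome, visit, draw or model term and controls no error across outcomes, so false-positive risk exceeds whatever per-test level is used

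*Combined protocol and SAP*

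**What the plan says.** The Data Analysis/Data Monitoring part of section E holds the whole statistical plan. Its scope is "All quantifiable results will be expressed as mean" with its standard error, analysed by repeated measures ANOVA. It adds: "All post-hoc tests will be conducted using a Scheffè test". No significance level, sidedness, primary outcome, time point or contrast is given.

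The objective, stated before section B, asks whether the supplement combined with exercise will produce "increased human peripheral blood sample levels of CD34+ and CD133+ adult stem cells and whether these stem cells display more protection against oxidative stress". It ranks none of these.

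The Blood Analysis part of section E sets out what is measured:

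- "flow cytometry to measure the stem cells including CD34+ and CD133+ cells at all blood draw time points", that is, before and after exercise at each of three visits;
- "serum measurements of biomarkers of inflammation and oxidative stress by the sponsor", with IL1β, IL4, IL6 and hsCRP named but no oxidative-stress marker;
- "A 5 ml SST tube will be collected for a lipid panel on the 1st blood draw of each session", with the panel's components not listed.

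The visit description in section E places both visit 1 blood draws before any supplement or placebo is handed out.

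**The concern.** A plan that tests everything and ranks nothing leaves open which result answers the trial's question. Scheffé's method may look like the safeguard, but it covers contrasts within a single fitted ANOVA. It does nothing across separate outcomes, and nothing across the several F tests involving arm in one model.

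With two arms, three visits and two draws per visit, the natural full model has four arm-related terms: arm, arm × visit, arm × draw, and arm × visit × draw. The plan does not say which of these bears on the objective.

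If the choice is made after the data are seen, an isolated significant result on one marker or one term is hard to interpret. That would be a loss here, because the objective already names two markers and both are measured at every draw.

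**Working it through.** The documents give no error rate to reproduce, so this check sizes the gap under stated assumptions.

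**Inputs from the documents**
- Six individually named measures: CD34+, CD133+, IL1β, IL4, IL6, hsCRP (Blood Analysis).
- Three visits and two draws per visit; lipids at the first draw only (section E).
- Two markers named in the objective for stem-cell levels.

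**Assumptions, not in the documents**
- Two-sided 5% per test.
- Four lipid components, giving 6 + 4 = 10 outcomes.
- A full arm × visit × draw model where four arm terms are counted, with those terms treated as independent.

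**Formulae.** For k independent tests with no true effect, the chance of at least one significant result in either direction is 1 − 0.95^k. In the direction favouring the supplement it is 1 − 0.975^k. The second formula treats each test as a single contrast. That is only approximate for the arm × visit and three-way terms, which have more than one degree of freedom.

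| Tests read | k | Either direction | Favouring supplement |
|---|---|---|---|
| CD34+ and CD133+, one test each | 2 | 1 − 0.95^2 = 9.8% | 1 − 0.975^2 = 4.9% |
| Six named measures, one test each | 6 | 1 − 0.95^6 = 26.5% | 1 − 0.975^6 = 14.1% |
| CD34+ and CD133+, four arm terms each | 8 | 1 − 0.95^8 = 33.7% | 1 − 0.975^8 = 18.3% |
| Ten outcomes, one test each | 10 | 1 − 0.95^10 = 40.1% | 1 − 0.975^10 = 22.4% |

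**Correlation.** Markers from the same blood sample are unlikely to be independent. Simulating normal test statistics with a common correlation of 0.5 gives 20.7% for six tests (10.4% favourable) and 28.7% for ten (14.4% favourable). These are lower than under independence but still well above 5% in either direction.

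**Which arm terms test treatment.** Suppose the supplement shifts a marker by δ at visits 2 and 3. At visit 1 the shift is zero, because nothing has yet been dispensed. The arm main effect averages the three visits: (0 + δ + δ)/3 = 0.67δ. The arm × draw term averages the pre-to-post difference over visits in the same way, so it also retains only two thirds of a constant effect. Both terms therefore dilute the treatment comparison, besides adding to the number of tests.

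**The case against.** A reader might infer that the plan tests at 5% and carries a 40 to 80% chance of a false claim of benefit. The documents do not support that, for four reasons.

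- No alpha is stated; 5% is an assumption.
- The formula behind such figures counts results in either direction. For results favouring the supplement, ten independent tests give 22%, and 31 tests (the count that gives 80% in either direction) give 54%.
- About 31 tests are reached only with an assumed lipid panel and a full factorial model that the plan never specifies. Independence is also the high-end assumption.
- The plan contains no rule that any one significant term supports the objective. The objective limits the question about cell levels to CD34+ and CD133+, and a lipid or IL4 result could not answer it. With one test for each of those two markers, the figure is 9.8%.

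It would also go too far to say that a positive result could not be told apart from chance, since effect size, strength of evidence and agreement between the two markers would still inform a reader.

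All of this stands, and it limits the size of the problem. It does not remove it: even for the two markers in the objective, the plan does not fix one test each. Some front and administrative pages were not available for this review, so a primary-outcome label there cannot be excluded. None appears in the objective, design or analysis text.

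**Conclusion.** The concern holds in a limited form. The plan fixes no alpha, primary outcome, visit, draw or arm term, and has no error control across outcomes, which Scheffé does not supply.

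At an assumed two-sided 5% with independent tests, the false-positive chance in either direction runs from about 10% (two objective markers, one test each) to about 40% (ten outcomes, one test each). The favourable-direction figures are roughly half of these. Positive correlation between markers reduces them all. The counts of four lipid components and four arm terms are assumptions, so these are illustrations of scale and not properties of the plan. This is a cheap improvement: the data needed are already being collected.

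**What to change.** Amend Data Analysis/Data Monitoring before unblinding to say the following.

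- Two-sided alpha is 5%.
- CD34+ and CD133+ are the two primary outcomes, at one pre-specified visit and draw. Visit 3 post-exercise is one example; the choice is the sponsor's, provided it is fixed in advance.
- For each marker, arms are compared by ANCOVA adjusted for the same participant's visit 1 value at the same draw, with Holm across the two markers. This uses the pre-supplement blood as a covariate instead of averaging it into the treatment effect.
- The other post-baseline visit and the remaining draws are secondary.
- Cytokines, hsCRP and lipids are reported as exploratory estimates with confidence intervals. Oxidative-stress protection, the second half of the objective, is treated the same way until a marker for it is named.

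The cost is one paragraph of text. Under Holm the smaller of the two primary p-values must meet 2.5% (5%/2), after which the other is tested at 5%. Outcomes outside the primary pair could no longer support confirmatory claims.

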BioVin® is much lower than reported side effects, we predict that there will be no adverse effects due to BioVin®. In addition, BioVin® is a full-spectrum grape extract and not just a concentrate of grape seed. Side effects and/or adverse events are not anticipated or expected, but the study coordinator will closely monitor for this possibility.

Green Tea Extract Adverse Events:

According to the NIH, more than five cups per day of green tea is considered “possibly unsafe” due to the side effects of the caffeine (23). These side effects can range from mild to serious and include headache, nervousness, sleep problems, vomiting, diarrhea, irritability, irregular heartbeat, tremor, heartburn, dizziness, ringing in the ears, convulsions, and confusion. In addition green tea seems to reduce the absorption of iron from food (23).

In clinical trials administering caffeinated green tea extracts, cancer patients who had an intake of 6 grams/day, in 3-6 divided doses, experienced mild to moderate gastrointestinal side effects, including nausea, vomiting, abdominal pain, and diarrhea (24,25). Some reported possible central nervous system symptoms, included agitation, restlessness, insomnia, tremors, dizziness, and confusion. These side effects were considered to be due to the caffeine in the green tea extract (25). In a four-week clinical trial that assessed the safety of decaffeinated green tea extracts (800 mg/day of EGCG) in healthy individuals, a few of the participants reported mild nausea, stomach upset, dizziness, or muscle pain (26).

Recently, oral use of green tea extracts (GTEs) has been associated with several instances of hepatotoxicity (27-30). Most affected patients were women, and many were consuming GTEs for the purpose of weight loss. Although hepatotoxicity in most cases resolved within four months of stopping GTE, there have been cases of positive rechallenge and liver failure requiring liver transplantation. A recent case report describes a case of acute liver failure requiring transplant in a woman consuming Green LiteJ capsules distributed by Origin Biomedicinals, Inc., Halifax, Canada (31). Since no other cause could be identified, the treating physicians concluded that the cause of the fulminant liver failure experienced by this subject was most likely related to the consumption of the over-the-counter GTE supplements for weight loss.

Potential Risks:

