At your 1st visit you will read and sign a consent form and give us some demographic information. We will check your blood pressure and glucose and BMI to make sure they are within normal limits. If they are not we will not be able to have you continue in the study. We will compensate you \$20.00 for your time if that happens.

If these tests are normal we will collect your blood, have you walk on the treadmill and then collect your blood again. You will receive your supplement of placebo to

NCT01847027

take for the next 4 weeks. If you are able to complete this visit you will receive \$40.00 to compensate you for time and travel.

If we are unable to collect your blood at any visit we will have to drop you from the study and you will receive partial compensation of \$20.00 for your time.

At your 2nd visit we will check your blood pressure & if normal we will collect your blood specimen followed by having you walk on the treadmill again. 5 to 15 minutes after that we will again collect the blood sample. You will receive \$60.00 compensation for completing this visit.

At your 3rd & last visit we will check your blood pressure & if normal we will collect your blood specimen followed by having you walk on the treadmill again. 5 to 15 minutes after that we will again collect the blood sample. You will receive \$80.00 compensation for completing this visit.

Do you have any questions or concerns? discuss as appropriate

If you are still interested I need to ask you some questions to determine if you qualify to participate in this study. If yes;

Age: _____
(Men/women age 50 to 70)

Difficult blood draw: _____
(exclude if self reported history of difficult veins/difficulty obtaining blood sample)

How much exercise: _____
(exclude if more than 2 sessions per week of strenuous exercise in the last month)

Food allergies _____
(exclude if any)

Diabetic: _____
(exclude if diabetic by diagnosis and/or use insulin or oral diabetic meds)

Hypertension: _____
(exclude if not controlled, under 180/100 not on meds, 150/90 on meds)

Unintentional weight loss/gain: _____
(exclude if lost or gained 10 or more pounds in the last 3 mos)

IRB APPROVED

JAN 04 2013

Current acute cold/flu other: _____
(exclude if yes)

NCT01847027

Hospitalization in last month: _____
(exclude if yes)

Chronic illness:

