(Exclude if severe co-morbid disease including cardiac, pulmonary, renal, hepatic, carotid, peripheral vascular disease, stroke, neurological, clotting disorders or active cancer (*defined as any condition that would cause severe limitations or inability to carry out usual activities of daily living*))

Antioxidant regimen or stem cell supplement in the 2 weeks prior to beginning this study:

_____ (exclude if took Alpha Tocepheral, Vitamin E, Ascorbic Acid, CoQ10)

Heart issues:

Self: _____ (exclude if cardiovascular event past 36 months)

Family: _____ (exclude if family hx sudden death or heart attacks before age 55)

Weight/height: _____ (exclude if BMI less than 20 or greater than 35 m/kg^2)

Other clinical trials: _____ (exclude if participated in a clinical trial in past 4 weeks)

Medications: _____
(exclude if methadone, insulin, anticoagulants, MAO's)

Any surgery planned: _____
(exclude for anticipated need for surgery of any type during study)

Blood donation: _____
(exclude if plan to donate blood or blood products during the study & for 30 days following the study)

Stomach problems: _____

(exclude if evidence of active peptic ulcer disease (vomiting of blood, dark blood in stools or stools that are black or tarry, nausea or vomiting, unexplained weight loss, unexplained appetite changes, abdominal pain))

GI bleeding: _____
(exclude if any hx GI bleed within the past 5 years)

Absorption problems: _____
exclude for:
Malabsorption Syndrome
Crohns
IBS
Ulcerative Colitis
gastric bypass

IRB APPROVED

JAN 04 2013

University of North Texas
Health Science Center

If all criteria met and still interested obtain:

NCT01847027

Mailing address: _____

Email: _____

Phone #'s: _____

Schedule for session #1 on: _____

Informed consent mailed for review: _____

Remind to fast (nothing but water after midnight) for blood draws

IRB APPROVED

JAN 04 2013

**University of North Texas
Health Science Center**

Subject ID: _____

Date: ____ / ____ / ____

NCT01847027

Demographic Form

This questionnaire asks you general demographic questions. We greatly appreciate your help.

1. Your birth-date is: _____, 19_____, making you: _____ years old

IRB APPROVED

2. Please select your ethnic origin:

Asian/Pacific Islander Native American Black

JAN 04 2013

White Hispanic Other, specify: _____

University of North Texas
Health Science Center

Your ethnicity:

Not Hispanic or Latino Hispanic or Latino

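### The screening script asks about food allergies but leaves out the other half of the same exclusion, intolerance of the capsule ingredients

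*Combined protocol and SAP*

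**What the plan says.** Section F, Exclusion Criteria, bars people who meet the description "Are unable to tolerate the ingredients in NutraStem® or placebo, or who self report food allergies". Either limb is enough to exclude. The opening paragraph of section F describes the screening script as a written tool derived from the eligibility criteria "that will be used to screen all potential participants".

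The script's matching item is headed "Food allergies", with an instruction to exclude for any. After its last question the line "If all criteria met and still interested obtain" introduces the contact details and the scheduling of the first session.

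For visit 1, the session table in section E lists "informed consent, demographic information collected, BP screening, diabetes screening, resting blood draw, exercise intervention, post exercise intervention blood draw, receive NutraStem or placebo". The script adds BMI to the visit 1 checks.

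On green tea extract, section E (Green Tea Extract Adverse Events) describes a four-week safety trial of a decaffeinated extract in healthy people, in which "a few of the participants reported mild nausea, stomach upset, dizziness, or muscle pain". It also describes liver injury with oral extracts and says that "there have been cases of positive rechallenge and liver failure requiring liver transplantation".

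**The concern.** The rule is written correctly, but the instrument meant to apply it drops half of it. A coordinator who runs the script exactly as written can schedule, and later supply with capsules, a person whom the protocol excludes.

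The closing paragraph of the exclusion list says the exclusions come from general safety concerns and from research on the ingredients, among other sources, so this criterion is there to protect participants. Section E also states that the combination had not been through human trials, which makes a person's own history with the single ingredients useful. The advice under Side Effects to stop the supplement helps only once someone has been exposed. What is at stake is avoidable exposure of a small number of people. No estimate or test in the trial depends on it.

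**Working it through.** The plan gives no figure for this point, so the check sets the texts side by side. A short piece of arithmetic on the caffeine content follows.

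**1. Criterion against script**

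| Limb of the exclusion | Script item |
|---|---|
| Self-reported food allergy | Yes: "Food allergies", exclude for any |
| Cannot tolerate an ingredient of NutraStem or placebo | None |

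**2. Could another script item catch it?**
- Stomach problems: limited to signs of active peptic ulcer disease.
- Absorption problems: a list of named bowel disorders and gastric bypass.
- Medications, and antioxidant or stem cell supplements: ask what the person takes, not how they reacted to it.
- Chronic illness: the instruction begins "Exclude if severe co-morbid disease including cardiac, pulmonary, renal, hepatic", but it is confined to conditions that severely limit daily activities. Section E says most green tea liver injury resolved within four months of stopping, so a recovered person would pass.
- The invitation to raise questions or concerns comes before the eligibility questions. Neither the script nor the recruitment flyer names a capsule ingredient, so a caller has little to react to.

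**3. Could a later step catch it?**
- Visit 1 screening is blood pressure, finger-stick glucose and BMI.
- The demographic form has no item on ingredients or reactions.
- The blood analyses are stem cell counts, a lipid panel and inflammation and oxidative stress markers. No liver test is listed.
- The exclusion at the investigator's discretion exists, but nothing prompts for the information it would need.

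**4. Which ingredients the criterion covers**
- Product: vitamin D3, grape extract, green tea extract, whole wild blueberry, carnosine and blueberry extract (6), plus magnesium stearate and cellulose under Other Ingredients (2), so 6 + 2 = 8.
- Placebo: 6 listed, of which 3 are colourings (a brown lake blend, a red dye, a blue lake) and 3 are fillers or excipients (MCC200, dicalcium phosphate, magnesium stearate).

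The list is short enough to read out on the telephone.

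**5. Dose context for green tea**

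Inputs, all from the green tea paragraphs of section E: 3.12 mg caffeine per fluid ounce, 8 oz per cup, 32 to 42 mg caffeine per dose of product, and a caution above five cups a day because of caffeine.
- Caffeine per cup: 3.12 × 8 = 24.96 mg, which matches the plan's figure.
- Product in cups, by caffeine: 32 / 24.96 = 1.28 to 42 / 24.96 = 1.68. This agrees with the plan's statement of less than 2 cups.
- If a dose means one capsule rather than the daily two (an assumption, to test the reading): 64 to 84 mg a day, or 2.56 to 3.37 cups.
- Five cups: 5 × 24.96 = 124.8 mg.

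On either reading the caffeine stays below the level of caution. By extract content the plan gives 3 to 4 cups, also below five. These comparisons concern caffeine and cup equivalents. They do not address the liver cases, for which the plan gives no dose.

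**The case against.** The strongest reply is that the protocol criterion is right and still binds the coordinator, and that a script based on the criteria need not repeat them word for word. The consent form is mailed before visit 1 and consent is taken before any capsule is given. It is a separate document that was not available here, and it may list the ingredients and side effects. All of this stands, and it limits the point to what the written screen does.

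The green tea evidence also needs care. The mild symptoms arose during a trial of 800 mg/day EGCG; they do not show how many people already know they are intolerant. Most of the liver cases were in women, and many were using extracts for weight loss. The plan's own dose figures point to low risk. That too stands. The adverse-event text shows only that there are reactions to an ingredient which a food-allergy question would not clearly draw out.

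Three stronger readings are tempting and are not supported:
- **That intolerant people are eligible, or will be dosed.** They are excluded by section F, and the unseen consent form or a volunteered remark may stop them.
- **That the screening promise in the Risk/Benefit Assessment is broken.** That sentence concerns medical conditions and medication use. It does not mention ingredient tolerance.
- **That a stated share of the ingredients escapes the food-allergy question.** Which ingredients a caller would count as food is guesswork; some callers may well report a dye reaction as a food allergy.

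**Conclusion.** The mismatch is real and can be read directly from the text: one limb of a two-limb exclusion is missing from the script, and no described step before dispensing supplies it. It is of low severity. The documents give no frequency of known intolerance, so the number affected cannot be estimated; it is probably small among up to 60 participants. Sample size, error rates and the efficacy analysis are unaffected.

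The conclusion rests on two assumptions: that the script is used as written, and that the consent form, which was not seen, does not already ask the question. If it does, only an administrative mismatch remains. The point is worth making because the correction is cheap.

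**What to change.** Add one item to the script beside the food-allergy question. In plain words it should name the product ingredients (green tea extract, grape extract, blueberry, carnosine, vitamin D3, magnesium stearate, cellulose) and the placebo's colourings and fillers. It should then ask about any known intolerance or previous significant reaction, including liver injury from green tea extract. Exclude anyone who cannot tolerate an ingredient and refer unclear answers to the investigator. Confirm the answer at visit 1 before dispensing. If the consent form already asks this, a script line pointing to it is enough.

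The cost is one question and one confirmation. The downside is that a few callers may become ineligible.
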